8.5.1. Safety Monitoring Rules for Liver Chemistry Tests

The following rules are adapted from the draft guidance for industry, "Drug-Induced Liver Injury: Premarketing Clinical Evaluation," issued by the U.S. Department of Health and Human Services, Food and Drug Administration, July 2009. For a definition of Baseline, please refer to guidance in Section 8.5 above.

All patients will have liver chemistry tests monitored every 14 days (± 2 days) for the first 3 months of the Treatment Period, and monthly thereafter during the Treatment Period. Upon completion of the study Treatment Period, liver chemistry tests should be monitored as per visit schedule in Appendix A.

In the event of appearance of symptoms or signs of hepatic injury (jaundice, fatigue, nausea, vomiting, right upper quadrant pain or tenderness, fever, rash, abnormal bleeding or bruising, or eosinophilia > ULN) liver enzymes and bilirubin should be tested as soon as possible (ideally within 3 days). Testing at a lab that is local to the patient is permissible for this purpose.

In the event of an ALT or AST measurement that is $> 3 \times ULN$ (or the greater of 2 × baseline value or 3 × ULN if the baseline value was > ULN) at any time during the study (Treatment or Post-Treatment Period), the initial measurement(s) should be confirmed as described in Section 8.5.

Frequency of Repeat Measurements: Patients with confirmed ALT or AST levels $> 3 \times$ ULN (or the greater of 2 × baseline value or 3 × ULN if the baseline value was > ULN) should have their liver chemistry tests (ALT, AST, alkaline phosphatase [ALP], INR and total bilirubin) retested at least once weekly until ALT and AST levels become $\le 1.2 \times$ ULN or $1.2 \times$ baseline if the baseline value was > ULN.

Further Investigation into Liver Chemistry Elevations: For patients with confirmed ALT or AST levels $> 3 \times ULN$ (or the greater of 2 × baseline value or 3 × ULN if the baseline value was > ULN), the following evaluations should be performed:

- Obtain a more detailed history of symptoms and prior and concurrent diseases
- Obtain further history for concomitant drug use (including non-prescription medications, herbal and dietary supplement preparations), alcohol use, recreational drug use, and special diets
- Obtain a history for exposure to environmental chemical agents and travel
- Serology for viral hepatitis (HAV IgM, HBsAg, HCV antibody, cytomegalovirus (CMV) IgM, and EBV antibody panel)
- Serology for autoimmune hepatitis (e.g., antinuclear antibody [ANA])

Additional liver evaluations, including gastroenterology/hepatology consultations, hepatic CT or MRI scans, may be performed at the discretion of the Investigator, in consultation with the Sponsor Medical Monitor. Repetition of the above evaluations should be considered if a patient's ALT and/or AST levels reach $\geq 5 \times$ ULN.

The Study Drug must be interrupted until all evaluations and consultation with the Sponsor Medical Monitor is complete.

Patients with confirmed ALT or AST levels $> 3 \times ULN$ (or the greater of 2 × baseline value or $3 \times ULN$ if the baseline value was > ULN) without an alternative explanation, and not meeting any of the Stopping Rules for liver chemistry elevations described in Section 8.6.1, must have Study Drug dose permanently reduced to 50 mg, if on an 80-mg dose. Patients on 50 mg should remain on the 50-mg dose.

All routine liver function test results will be reviewed on an ongoing basis at the weekly safety review by the Sponsor Medical Monitor.

All lab alerts for abnormal liver function tests must be promptly reviewed by the Investigator (within 48 hours of receipt) and Medical Monitor(s) (within 24 hours of receipt) as described in Section 6.2.1.

Lab alerts for abnormal liver chemistry tests will be issued for: 1) ALT or $AST > 3 \times ULN$; 2) ALT or $AST > 2 \times$ baseline; 3) total bilirubin > ULN; 4) ALP > ULN. These alert levels are set to anticipate the risk of a combined elevation of aminotransferases and bilirubin as per the FDA Guidance referenced in Section 8.5.1 above.

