5.2. Exclusion Criteria

- 1. Clinically significant abnormalities in medical history (e.g., previous acute coronary syndrome within 6 months of Screening, major surgery within 3 months of Screening) or physical examination
- 2. Active pancreatitis within 4 weeks prior to Screening
- 3. Screening laboratory results as follows, or any other clinically significant abnormalities in screening laboratory values that would render a patient unsuitable for inclusion
 - a. Platelet count < 100K/mm³ at Screening or Qualification. If the platelet count is < 100K/mm³ up to 2 additional tests may be performed to qualify at both Screening and Qualification.
 - b. Alanine aminotransferase (ALT) or aspartate aminotransferase (AST) > 3.0 × upper limit of normal (ULN)
 - c. Total bilirubin > ULN unless due to Gilbert's syndrome
 - d. Estimated GFR < 45 mL/min/1.73 m² [as determined by the CKD-EPI formula for creatinine clearance; (Levey et al. 2009)]
 - e. Urine protein/creatinine ratio (UPCR) ≥ 500 mg/g, or urine albumin/creatinine (UACR) ratio ≥ 300 mg/g
- 4. Uncontrolled arterial hypertension (BP > 160/100 mm Hg)
- 5. History of bleeding diathesis or coagulopathy or clinically significant abnormality in coagulation parameters at Screening
- 6. Active infection requiring systemic antiviral or antimicrobial therapy that will not be completed prior to Study Day 1 or active Covid-19 infection with or without therapy that will not be resolved by Study Day 1
- 7. Active infection with human immunodeficiency virus (HIV), hepatitis C or hepatitis B diagnosed by initial serological testing and confirmed with RNA testing, or prior treatment for hepatitis C. Patients at Screening who test positive by serology, but negative by RNA may be allowed in consultation with the Sponsor Medical Monitor
- 8. Malignancy within 5 years, except for basal or squamous cell carcinoma of the skin or carcinoma *in situ* of the cervix that has been successfully treated. Patients with a history of other malignancies that have been treated with curative intent and which have no recurrence within 5 years may also be eligible if approved by the Sponsor Medical Monitor
- 9. Blood donation of 50 to 499 mL within 30 days of Screening or of > 499 mL within 60 days of Screening

- 10. Treatment with another investigational drug (non-oligonucleotide), biological agent, or device within 1 month of Screening, or 5 half-lives of investigational agent, whichever is longer

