8.5. Safety Monitoring Rules

Stopping rules are described below in Section 8.6.

Please refer also to the 'Guidance for Investigator' section of the Investigator's Brochure.

- For the purposes of safety monitoring Baseline is defined as the average of the Day 1 pre-dose assessment and the last measurement prior to Day 1.
- In addition to the standard monitoring of clinical safety parameters, the following guidelines are provided for the monitoring of selected parameters chosen based on preclinical and clinical observations.
- In case of discrepancy between the test results from 2 sources, such as between the central and local lab, safety-mandated action must be initiated based on the more critical (lower or higher, as relevant) of the 2 values.

Confirmation Guidance: At any time during the study (Treatment or Post-Treatment Periods), the clinical laboratory results meeting any of the safety monitoring criteria presented below **must be confirmed** by performing measurements (ideally in the same laboratory that performed the

initial measurement) on new specimens. All new specimen collections should take place as soon as possible (ideally within 3 days but no later than 7 days of the initial collection). For stopping rules, if the initial laboratory result is observed during the Treatment Period, the results from the retest **must be available** prior to administering the next dose of Study Drug.

Re-dosing Guidance: In the event the initial laboratory result meets a stopping criterion, the results from the retest **must be available and reviewed by a Medical Monitor** prior to administration of the next dose of Study Drug (ISIS 678354 or placebo). In general, patients who do not meet the stopping rules based upon retest may continue dosing. However, the Investigator and the Sponsor Medical Monitor (or appropriately qualified designee) should confer as to at which dose Study Drug should be restarted, and whether additional close monitoring of the patient is appropriate. If any of the stopping criteria described below (refer to Section 8.6.1 through Section 8.6.3) are met, the patient will be permanently discontinued from further treatment with Study Drug (ISIS 678354 or placebo), evaluated fully as outlined below and in consultation with the Sponsor Medical Monitor or appropriately qualified designee, and will be followed up in accordance with Section 8.8 of the protocol.

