8.6.1. Stopping Rules for Liver Chemistry Elevations

All cases of confirmed laboratory results meeting any of the following criteria, but having an alternative etiology such as congestive heart failure, introduction of a new drug, some identified biliary tract issues etc., must be reviewed by local hepatologist, the DSMB hepatologist, and the decision to restart the Study Drug must be made upon reaching a general agreement between consulting hepatologist, the DSMB hepatologist, and the Sponsor Medical Monitor that the alternative etiology is well supported as the likely cause, and when ALT and AST levels become

\leq 3 × ULN. Until this evaluation is completed and a decision agreed upon, the treatment with the Study Drug will remain interrupted.

In the event of confirmed laboratory results meeting any of the following criteria, **and the event is without an alternative explanation as discussed with the Medical Monitor**, dosing of a patient with Study Drug (ISIS 678354 or placebo) will be stopped permanently; values that are not confirmed due to failure to retest or missing lab values will be presumed confirmed:

- 1. ALT or $AST > 8 \times ULN$, which is confirmed
- 2. ALT or AST > 5 × ULN, which is confirmed and persists for \ge 2 weeks
- 3. ALT or AST > $3 \times$ ULN (or the greater of $2 \times$ baseline value or $3 \times$ ULN if the baseline value was > ULN), which is confirmed **and** total bilirubin > $2 \times$ ULN or INR > 1.5
- 4. ALT or AST > 3 × ULN (or the greater of 2 × baseline value or 3 × ULN if the baseline value was > ULN), which is confirmed, **and** the new appearance (i.e., onset coincides with the changes in hepatic enzymes) of fatigue, nausea, vomiting, right upper quadrant pain or tenderness, fever, rash, and/or concomitant eosinophilia (> ULN)

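### For Baseline ALT or AST above 2.5 × ULN, the weekly-retest trigger in 8.5.1 lies above the 5 × ULN of stopping criterion 2, so after month 3 no rule calls for the 2-week value that criterion needs

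*Combined protocol and SAP*

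**What the plan says.** **Trigger (protocol 8.5.1).** A confirmed ALT or AST above 3 × ULN leads to at least weekly retests. If Baseline is above ULN, the level is instead "the greater of 2 × baseline value or 3 × ULN if the baseline value was > ULN". The same level governs the confirmation sentence, the cause work-up and the reduction from 80 to 50 mg.

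**Baseline (8.5).** For safety monitoring, "Baseline is defined as the average of the Day 1 pre-dose assessment and the last measurement prior to Day 1". Exclusion 3b in 5.2 rules out a Screening ALT or AST above 3.0 × ULN.

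**Stopping rule (8.6.1).** Criterion 2 reads "ALT or AST > 5 × ULN, which is confirmed and persists for" at least 2 weeks, with no Baseline term. Criterion 1 is above 8 × ULN. Criteria 3 and 4 carry the Baseline clause of 8.5.1.

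**Routine tests (8.5.1, Appendix A).** Liver tests run every 14 days for 3 months and then monthly, on the dosing visits. Samples are taken before the dose.

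**Existing safeguards.**
- 8.5 asks for a confirming specimen, "ideally within 3 days but no later than 7 days of the initial collection". For a result that meets a stopping criterion, a Medical Monitor must review the retest before the next dose.
- 8.5 adds: "In general, patients who do not meet the stopping rules based upon retest may continue dosing". The sentence after it asks the Investigator and Sponsor Medical Monitor to confer on the restart dose and on whether to watch the patient more closely.
- 8.5.1 says that repeating the evaluations is to be considered from 5 × ULN upward, whatever the Baseline. It also sends an alert above 3 × ULN and has the Medical Monitor review liver results weekly.
- 8.6.1 states that "values that are not confirmed due to failure to retest or missing lab values will be presumed confirmed".

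**The concern.** Monitoring should start at a lower level than stopping, so that the data a stopping rule needs are already being collected when it might apply. The text of 8.5.1 points the same way: it speaks of repeating evaluations from 5 × ULN, which presumes a first round at a lower value. For a high Baseline the order reverses. The fixed stopping level is passed first, and the tests that would show 2 weeks of persistence are tied to a higher level. At stake is how soon criterion 2 is recognised in a patient whose ALT or AST stays above 5 × ULN.

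**Working it through.** The plan gives no figure of its own on this point, so the check compares the two thresholds and then the calendar.

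**Thresholds.** Let s be the last value before Day 1 and d the Day 1 value, both in × ULN (8.5). Then Baseline b = (s + d)/2. For b > 1 the 8.5.1 trigger is max(2b, 3). It exceeds 5 when 2b > 5, that is b > 2.5. The lower edge of the gap, as a multiple of Baseline, is 5/b, and the upper edge is 2.

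| Baseline b | Trigger max(2b, 3) | Gap (× ULN) | Gap (× Baseline) |
|---|---|---|---|
| 2.0 | 4.0 | none | none |
| 2.5 | 5.0 | none | none |
| 2.6 | 5.2 | 5.0 to 5.2 | 1.92 to 2.0 |
| 2.75 | 5.5 | 5.0 to 5.5 | 1.82 to 2.0 |
| 3.0 | 6.0 | 5.0 to 6.0 | 1.67 to 2.0 |

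The limit of 3.0 in 5.2 is on the Screening value. If Day 1 were higher, for example s = 3.0 and d = 4.0 (an assumption), then b = 3.5 and the trigger would be 7.0.

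**Which stopping rule can act in the gap.** Criterion 1 needs more than 8 × ULN. Criteria 3 and 4 need more than max(2b, 3), which is the top of the gap. Within the gaps shown, only criterion 2 can apply, and it needs a value at 2 weeks.

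**Calendar.** In the first 3 months the 14-day schedule gives that value. From Week 17 to Week 49 there are nine monthly visits (17, 21, 25, 29, 33, 37, 41, 45, 49). They bound 8 of the 13 − 1 = 12 dosing intervals. An example in nominal days from Appendix A, starting at Week 29:
- Day 197: sample and dose. The alert arrives by 197 + 2 = 199 (6.2.1).
- Confirming sample by 197 + 7 = 204.
- With weekly retests, further values by 204 + 7 = 211 and 211 + 7 = 218. Two weeks have passed by Day 211 if counted from the first value, or by Day 218 if counted from the confirming one.
- Without them, the next scheduled sample is on Day 225, with its result by 225 + 2 = 227.

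The delay in the 2-week value is 225 − 218 = 7 to 225 − 211 = 14 days.

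**After the fix.** The retest trigger becomes min(5, max(2b, 3)). That is 4.0 at b = 2.0 and 5.0 at b = 2.5, both unchanged, and 5.0 at b = 2.6, 2.75 and 3.0. No gap remains.

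**The case against.** The strongest reply is that the plan handles this patient case by case. An alert goes out, a Medical Monitor reviews liver results weekly, and 8.5 has the Investigator and Medical Monitor consider closer follow-up. 8.5.1 has its own prompt at 5 × ULN that ignores Baseline. The weekly retests and cause work-up are worded as recommendations even above the trigger. The Investigator may interrupt dosing at any time, and no Phase 2 patient met a liver monitoring rule (2.3.4). All of this stands, and it limits the harm. None of it schedules a value at 2 weeks. The presumption in 8.6.1 covers missing confirmation and says nothing about persistence.

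One could also read 8.5.1 as triggered by 3 × ULN alone. The Baseline clause would then do nothing, since the greater of the two values is never below 3 × ULN. SAP 4.10.5 also has a category that requires both 3 × ULN and 2 × Baseline.

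Two stronger readings are tempting, and the documents do not support them.
- A reader might infer that the plan permits the Day 225 dose unchecked. The permission in 8.5 is for patients whose retest shows that no stopping rule is met. A retest at 7 days or less cannot show that for a 2-week criterion, so 8.5 does not clearly allow the dose.
- A reader might infer that interruption, work-up and dose reduction should also begin at 5 × ULN. At Baseline 3.0 that is a rise of 1.67 to 2.0 × Baseline, within the 1.5 to 3.0 × Baseline that Appendix D grades Mild. The reduction to 50 mg is permanent, and 8.7 discourages dose changes before Month 6. That trade-off is debatable, and the missing 2-week value does not settle it.

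**Conclusion.** The inversion is real for Baseline ALT or AST above 2.5 × ULN. At Baseline 3.0 the gap runs from 5.0 to 6.0 × ULN. It matters after the first 3 months, when a 2-week value depends on judgment. The worst case is a 7- to 14-day delay in recognising criterion 2, and possibly one further dose.

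This rests on reading the Baseline clause as replacing 3 × ULN and on nominal visit days. The documents give no count of patients with Baseline above 2.5 × ULN. That few if any of about 60 would be affected is an assumption. The point is a cheap improvement of low severity. The study ended in October 2023 according to the lay summary, so its use lies in any later protocol that takes over these rules.

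**What to change.** Make two additions in 8.5.1:
- In the confirmation sentence, state that any ALT or AST above 5 × ULN is to be confirmed, whatever the Baseline.
- Under the repeat-measurement rule, state that such a value, once confirmed, is retested at least weekly until criterion 2 is met or ruled out.

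Leave the triggers for work-up, interruption and dose reduction as they are, and leave every 8.6.1 criterion unchanged. Nothing changes at Baseline 2.5 × ULN or below, where the trigger is already at or under 5 × ULN.

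The cost is a few extra chemistry samples in rare patients. Some can be taken at the 14-day hematology draws that 6.2.1 and 8.5.3 already require. In the example, Day 211 is 197 + 14 and so falls on that schedule.

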8.5.2. Safety Monitoring for Renal Function

While on treatment, all patients will have renal function tests monitored every 14 days (\pm 2 days) for the first 3 months of the Treatment Period, and monthly thereafter during the Treatment Period. Upon completion of the study Treatment Period, renal function tests should be monitored as per visit schedule in Appendix A.

In the event of appearance of symptoms or signs consistent with renal dysfunction such as hematuria, polyuria, anuria, flank pain, new-onset hypertension, nausea and/or anorexia, renal

function should be tested as soon as possible (ideally within 3 days). Testing at a lab that is local to the patient is permissible for this purpose.

Renal function surveillance will include serum creatinine and urinalysis including UACR, UPCR, urinary red blood cells (RBC). The assessment of serum creatinine and urinalysis more frequently than every 14 days will be guided by consultation with a local nephrologist.

All renal function test results will be reviewed on an ongoing basis by the Medical Monitor.

All results of renal function tests must be reviewed promptly (within 48 hours of receipt) by the Investigator or the designee to ensure that the result has not met the stopping rules per Section 8.6.2.

If any of the below criteria are met, an alert will be issued and treatment with Study Drug should immediately be interrupted, and the Study Medical Monitor should be informed. In addition, the result should be confirmed as soon as possible (as described in Section 8.5), but no later than 7 days after the initial event.

- eGFR (by CKD-EPI formula) decrease from Baseline > 25%
- Urine albumin/creatinine ratio (UACR) > 300 mg/g, or > 50% Baseline whichever is greater
- UPCR > 500 mg/g, or > 50% Baseline whichever is greater

If the confirmatory test is negative (i.e., repeat sample taken with 7 days is within normal limits), the patient may continue treatment with Study Drug upon consultation with the Medical Monitor. If results from additional testing confirm the initial abnormal lab result, the site will obtain any additional lab assessments necessary to determine any alternative etiologies that may account for the abnormal result, upon consultation with the Medical Monitor.

The Investigator should also review the patient's concomitant medications for potentially nephrotoxic agents, and, with the results of these evaluations, review any decision to continue or discontinue the patient in consultation with the Medical Monitor. Any decision taken by the Investigator to discontinue Study Drug will be made taken into account all available and relevant data. In addition, the decision to discontinue Study Drug may also be based on lesser changes in these parameters observed in isolation or in association with other renal-related abnormalities.

Further instruction regarding treatment interruption and/or permanent stopping of Study Drug can be found in Section 8.6.2.

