8.6.2. Stopping Rules for Renal Function Test Results

In the event that the any of the renal monitoring rules summarized in Section 8.5.2 are met, treatment with Study Drug should immediately be interrupted and the abnormal result should be confirmed as soon as possible, but no later than 7 days after the initial event. In addition, upon consultation with the Medical Monitor, the site will obtain any additional lab assessments necessary to determine any alternative etiologies that may account for the abnormal result. If results from additional testing confirm the initial abnormal lab result(s) described in Section 8.5.2, and additional evaluations regarding etiology accounting for these abnormalities are completed, future treatment of the patient will be determined per the guidelines below:

- An alternative etiology is identified that may account for abnormal results
 - Patient will have treatment with Study Drug interrupted until either:
 - Lab values have returned to baseline, and/or
 - Alternative etiology has resolved/recovered, AND
 - Study Medical Monitor has approved Study Drug treatment to resume
- An alternative etiology has not been identified that may account for abnormal results:
 - o Patient will be permanently withdrawn from Study Drug treatment

The follow-up schedule and frequency of renal function monitoring after the initial event will be determined by the Medical Monitor in consultation with the Investigator. The Investigator should consider consulting a local nephrologist for any change of renal function that presents a concern. If a renal biopsy is performed, a sample specimen should be made available for examination by an independent renal pathologist who has been engaged by the Sponsor to review such specimens.

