8.8. Discontinuation of Study Drug

A patient must permanently discontinue Study Drug treatment for any of the following:

- The patient becomes pregnant. Report the pregnancy according to instructions in Section 9.5.4
- The patient withdraws consent
- The patient experiences an AE that necessitates permanent discontinuation of Study Drug
- The patient develops laboratory test abnormalities that meet any of the stopping rules listed in Section 8.6.1 to Section 8.6.3
- The patient experiences an AE that necessitates unblinding of the Investigator or Sponsor to the patient's treatment assignment

The reason for discontinuation of Study Drug must be recorded in the eCRF and source documentation.

8.8.1. Follow-up Visits for Early Termination from Treatment Period or Post-Treatment Follow-up Period

Any patient who discontinues early from the Treatment Period should be strongly encouraged to attend applicable landmark visits at Weeks 23, 25, 27 and Weeks 51 and 53 (calculated based on the time elapsed since Day 1) to collect fasting lipid panels and conduct safety assessments in accordance with Appendix A. Any patient who discontinues early from the Post-Treatment Follow-up Period should be strongly encouraged to complete follow-up study visits, procedures and observations in accordance with Appendix A.

Any patient who discontinues early from the Treatment Period or from Post-Treatment Follow-up Period should be followed as per the platelet monitoring rules shown in Table 2, Section 8.6.3 for the first 6 weeks Post-End of Treatment Period and then at 8 and 13 weeks Post-End of Treatment Period (as per visit schedule).

If a patient discontinues early from the Treatment Period and declines or is unable to participate in the above, an ET visit (Week 53 visit assessments) should be performed at the time of withdrawal, and ideally within 2 weeks from the last dose of Study Drug, and patients should start the 13-week Post-Treatment Follow-up Period to collect the study assessments in accordance with the Schedule of Procedures in Appendix A.

If the patient discontinues early from the Post-Treatment Follow-up Period and declines or is unable to participate in the above, a final visit (assessments from Week 13 of the Post-Treatment Follow-up Period) should be performed at the time of withdrawal.

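### In Section 8.5.2 a repeat eGFR in the normal range counts as negative even when it still confirms the > 25% fall from Baseline that Section 8.6.2 acts on

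*Combined protocol and SAP*

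**What the plan says.** Protocol Section 8.5.2 lists three renal criteria, any of which leads to an alert, immediate interruption of Study Drug and a repeat test within 7 days. The eGFR criterion is purely relative: "eGFR (by CKD-EPI formula) decrease from Baseline > 25" per cent. The UACR and UPCR criteria each take the greater of an absolute level (300 and 500 mg/g) and a Baseline-based level.

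One sentence, naming no analyte, then covers a favourable repeat: "If the confirmatory test is negative (i.e., repeat sample taken with 7 days is within normal limits), the patient may continue treatment" once the Medical Monitor has been consulted. The next sentence covers a repeat that confirms the first result and starts the search for other causes. The section ends with a pointer: "Further instruction regarding treatment interruption and/or permanent stopping of Study Drug can be found in Section 8.6.2".

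Section 8.6.2 begins its consequences with "If results from additional testing confirm the initial abnormal lab result(s) described in Section 8.5.2". If another cause is found, drug stays interrupted until values return to baseline and/or the cause resolves, and the Medical Monitor approves resumption. If none is found: "Patient will be permanently withdrawn from Study Drug treatment". Section 8.8 makes discontinuation mandatory when "The patient develops laboratory test abnormalities that meet any of the stopping rules listed in Section 8.6.1 to Section 8.6.3".

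Section 8.5 gives general guidance. When a first result meets a stopping criterion, the retest "must be available and reviewed by a Medical Monitor" before the next dose, and "In general, patients who do not meet the stopping rules based upon retest may continue dosing".

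**The concern.** The alert asks whether eGFR has dropped relative to the patient's own Baseline. The definition of a negative repeat asks whether eGFR is in the population normal range. A patient who starts with a high eGFR can fail the first test and pass the second with the same value. Section 8.5.2 then allows dosing to continue, while Section 8.6.2 requires interruption or permanent withdrawal. In 8.5.2 the work-up for other causes belongs to the confirmed branch, so the negative label would also bypass it.

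Other parts of the protocol judge a repeat against the criterion that raised the alert. Section 8.5 refers to the stopping rule, and Section 8.5.1 speaks of confirmed ALT or AST at the alert threshold itself. The renal sentence departs from that pattern and introduces its definition with an explicit i.e., so it cannot be read as a loose example.

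**Working it through.** The plan has no figure to reproduce here. The check is whether the two descriptions of a repeat eGFR can both be true.

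**Inputs**
- Trigger: fall > 25%, so value < 0.75 × Baseline (Section 8.5.2).
- Negative repeat: value ≥ L, the lower normal limit (Section 8.5.2). The documents give no L for eGFR. Values of 60, 75 and 90 mL/min/1.73 m² are assumed.
- Baseline: mean of the Day 1 pre-dose value and the last earlier value (Section 8.5).
- Eligibility: eGFR < 45 excluded, no upper limit (Section 5.2, criterion 3d).

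**Overlap.** Both descriptions hold when L ≤ repeat < 0.75 × Baseline. That range is non-empty only if Baseline > L/0.75. The largest fall that can still be called negative is 1 − L/Baseline.

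| Assumed L | Overlap needs Baseline above | Example Baseline | Repeats meeting both | Largest fall still negative |
|---|---|---|---|---|
| 60 | 60/0.75 = 80 | 100 | 60 to < 75 | 1 − 60/100 = 40% |
| 60 | 80 | 120 | 60 to < 90 | 1 − 60/120 = 50% |
| 75 | 75/0.75 = 100 | 120 | 75 to < 90 | 1 − 75/120 = 37.5% |
| 90 | 90/0.75 = 120 | 125 | 90 to < 93.75 | 1 − 90/125 = 28% |

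**An unchanged repeat.** Take L = 60, Baseline 120 and a first value of 80. The fall is 1 − 80/120 = 33.3%, so the alert is raised. A repeat of exactly 80 reproduces the finding and is also ≥ 60. It is confirmed and negative at once.

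**Against the SAP's reporting categories.** SAP Section 4.10.5 tabulates eGFR reductions of ≥ 25%, 30%, 50% and 75%. With L = 60, a negative repeat can reach the ≥ 30% category from Baseline 60/0.70 = 85.7 and the ≥ 50% category from 60/0.50 = 120. With L = 90 the corresponding Baselines are 90/0.70 = 128.6 and 90/0.50 = 180. These are reporting bins, not dosing rules, and SAP Section 4.2.2 takes the last pre-dose value as Baseline, so the match is approximate.

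**UACR and UPCR.** Their triggers can never be below 300 and 500 mg/g. Taking the lowest SAP shift categories (< 30 and < 150 mg/g) as a proxy for normal, no repeat can be both normal and above the trigger. This holds whether the Baseline term is read as 0.5 × or 1.5 × Baseline. The same sentence instead leaves a gap for these tests: repeats from 30 to 300 mg/g (UACR) or 150 to 500 mg/g (UPCR) are neither negative nor confirming. A low-Baseline eGFR has a similar gap. At Baseline 50 with L = 60, a repeat of 45 is a fall of only 10% but is not in the normal range.

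**The case against.** The strongest reply is that the protocol, read as a whole, already gives the right answer.

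- A repeat still more than 25% below Baseline is itself a renal result that meets the 8.5.2 criterion, and the interruption instructions in 8.5.2 and 8.6.2 are not limited to a first sample.
- Section 8.5.2 requires every renal result to be checked against the 8.6.2 stopping rules, and it sends the reader to Section 8.5 for how to confirm a result. Section 8.5 judges the retest by the stopping rule.
- The 8.5.2 sentence only permits continuation, after consultation. Sections 8.6.2 and 8.8 are mandatory. Section 8.5.2 also lets the investigator stop drug for lesser changes.

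All of this stands, and it is why harm is unlikely. It does not remove the conflict. No text says that the general guidance overrides the specific renal definition, and consultation does not tell the Medical Monitor which test governs.

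A second reply is that the overlap comes from reading two paired sentences by different standards: a normal value cannot confirm an abnormal one. This fails for eGFR. Section 8.6.2 refers back to the results described in 8.5.2, where the eGFR abnormality is the decline. The value that raised the alert may itself be in the normal range, as in the 80-and-80 example.

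A third reply is that L is not in the documents and no Baseline eGFR distribution is given. This is correct. The overlap exists at every L tried, but it is narrow at L = 90, and the number of patients in it cannot be estimated.

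**Conclusion.** Wrong as written, low severity. The sentence defining a negative repeat covers all three renal tests, but only for eGFR can one repeat be both negative under 8.5.2 and confirmed under 8.6.2. The overlap requires Baseline eGFR above L/0.75, that is above 80 to 120 for an assumed L of 60 to 90. Within it, the fall that can be labelled negative ranges from just over 25% to 1 − L/Baseline.

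Three stronger readings are tempting, and the documents do not support them:

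- A reader might infer that patients with a persistent renal decline would be kept on drug. The Section 8.5 retest guidance, renewed interruption when the repeat still meets the criterion, mandatory 8.6.2 and 8.8, and Medical Monitor review all work against that.
- A reader might infer the same contradiction for UACR and UPCR. Their absolute floors rule it out.
- A reader might infer an effect on the trial's results. No endpoint or planned analysis depends on this sentence.

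**What to change.** Make two edits.

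- Section 8.5.2: state that an eGFR retest is negative only if the repeat, taken within 7 days, is no longer more than 25% below Baseline.
- Section 8.6.2: state that a result is confirmed when the repeat still meets the 8.5.2 criterion that triggered the alert.

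Keep Medical Monitor consultation. For eGFR, the dividing line then becomes 0.75 × Baseline at every Baseline, so no repeat is both negative and confirmed. Using that line in place of the normal range also closes the low-Baseline gap.

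Leave the UACR and UPCR retest standard as it is unless the sponsor chooses to align it with Section 8.5. Applying the same wording to those tests would close their gap, but it would loosen the standard: a repeat that is abnormal yet not above 300 or 500 mg/g would become negative. That choice should be made openly.

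The cost is one sentence and one clause, made through the amendment process in Section 12.1, with no new tests, visits or data.
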